10.0 Treatment Compliance

All study drugs must be kept in a secure location under appropriate storage conditions. Access must be restricted to authorized personnel. The intake of all study drugs will be recorded in the Case Report Form (CRF) in a medication administration log. Patients will take home the medication needed until next protocol visit in a safe container box. Used vials must be returned for accountability. The medication provided for this study is for use only as directed in the protocol. GWU Medical Faculty Associates will be responsible for the storage, handling, and dispensing of study drug. The GWU Medical Faculty Associates will monitor all documentation related to drug handling activities to ensure adherence to proper procedures.

All unused study drugs must be returned to GWU Medical Faculty Associates for reconciliation and accountability and should be destroyed at the study site by authorized personnel according to approved procedures or collected by the monitor for disposal.

Study drugs are to be prescribed only by a physician named in the study form. Under no circumstances will the investigator allow the study drug to be used other than as directed by the protocol.

11.0 SAFETY ISSUES

SAFETY ASSESSMENTS

General

Safety assessments will include adverse events, vital signs, physical examination findings, laboratory parameters (hematology, serum chemistry, including BUN, creatinine, urinalysis) and NCI common toxicity safety assessment.

12.0 ADVERSE EVENT REPORTING

12.1 Adverse Events

An adverse event (AE) is any reaction, side effect, or other undesirable or unexpected experience that occurs in conjunction with the use of the study drug, whether or not the experience is considered drug-related. New or worsening signs and symptoms of underlying or emerging disease are also considered adverse events. Adverse events will be tracked through routine communication with the subjects and the family.

12.1.1 Study Drug Relationship

The clinical site investigator will determine which events are associated with the use of study drug. For reporting purposes, an AE should be regarded as possibly related to the use of the investigational product if the investigator believes:

- There is a clinically plausible time sequence between onset of the AE and abatacept administration; and/or
- There is a biologically plausible mechanism for causing or contributing to the AE; and
- The AE cannot be attributed solely to concurrent/underlying illness, other drugs, or procedures.

An AE is deemed associated with the use of the study drug “if there is a reasonable possibility that the AE may have been caused by the drug” (21 CFR 312.32)

12.2 Immediately Reportable Events

There are 2 categories of medical events that could occur during participation in this clinical trial that must immediately be reported to [name]. The categories are as follows:

- Death or other serious adverse experience (SAE)
- Pregnancy

A serious adverse event is any experience that results in one of the following: hospitalization or prolonged hospitalization, a life threatening event resulting in: death, significant or permanent disability, congenital anomaly/birth defect (in the case of unanticipated birth to a study participant), or requires intervention to prevent permanent damage.

[name] will distribute reports of SAEs, which are both unexpected and related to the study medication, to the DSMB, the FDA, BMS Drug Safety, and to the Institutional Review Board. Reporting of adverse events will follow all applicable regulatory laws, guidelines and timeframes. Procedures for reporting adverse events are detailed in the Manual of Operations for this study.

12.3 Physical Examination Observations

Baseline observations from the Screening physical examination that worsen during the study will be recorded on the Adverse Event CRF page. Every effort should be made for the same physician to conduct all physical examination assessments on each subject. Care will be taken to avoid reporting worsening of initial physical examination observations which may result only from differing medical opinions when the same physician is not available to conduct pre-study, interim and end of study physical examinations.

A Serious Adverse Event (SAE) is any untoward medical occurrence that at any dose:

- Results in death
- Is life-threatening (defined as an event in which the subject was at risk of death at the time of the event; it does not refer to an event which hypothetically might have caused death if it were more severe)
- Requires inpatient hospitalization or causes prolongation of existing hospitalization (see note below for exceptions)
- Results in persistent or significant disability/incapacity
- Is a congenital anomaly/birth defect

- Is an important medical event, defined as a medical event that may not be immediately life-threatening or result in death or hospitalization but, based on appropriate medical and scientific judgment, may jeopardize the subject or may require intervention (e.g., medical, surgical) to prevent one of the other serious outcomes listed above. Examples of such events include but are not limited to intensive treatment in an emergency department or at home for allergic bronchospasm; blood dyscrasias or convulsions that do not result in hospitalization. Potential drug induced liver injury (DILI) is also considered an important medical event (see Section 7.6 for the definition of potential DILI).
- Suspected transmission of an infectious agent (e.g., any organism, virus or infectious particle, pathogenic or non-pathogenic) via the study drug is a SAE.
- Although pregnancy, overdose and cancer are not always serious by regulatory definition, these events must be handled as SAEs. Following the subject's written consent to participate in the study, all SAEs, whether related or not related to study drug, must be collected, including those thought to be associated with protocol-specified procedures. All SAEs must be collected that occur within 30 days of discontinuation of dosing. The investigator should report any SAE occurring after these time periods that is believed to be related to study drug or protocol-specified procedure. An SAE report should be completed for any event where doubt exists regarding its status of seriousness. If the investigator believes that an SAE is not related to study drug, but is potentially related to the conditions of the study (such as withdrawal of previous therapy, or a complication of a study procedure), the relationship should be specified in the narrative section of the SAE Report Form.

All SAEs, whether related or unrelated to abatacept, and all pregnancies must be reported to BMS and the Data Safety Monitoring Board (by the investigator or designee) within 24 hours.

All SAEs should be reported via confirmed facsimile (fax) transmission, or scanned and reported via electronic mail to:

SAE Email Address: [contact]

SAE [contact]

For studies conducted under an Investigator IND, any event that is both serious and unexpected must be reported to the Food and Drug Administration (FDA) as soon as possible and no later than 7 days (for a death or life-threatening event) or 15 days (for all other SAEs) after the investigator's or institution's initial receipt of the information. BMS will be provided with a simultaneous copy of all adverse events filed with the FDA.

SAEs should be reported on MedWatch Form 3500A, which can be accessed at: <http://www.accessdata.fda.gov/scripts/medwatch/>.

MedWatch SAE forms should be sent to the FDA at:

MEDWATCH

[name]

[name]

Fax: [name] ([name])

<http://www.accessdata.fda.gov/scripts/medwatch/>

All SAEs should simultaneously be faxed or e-mailed to BMS at:
Global Pharmacovigilance & Epidemiology
Bristol-Myers Squibb Company
[contact]
Email: [contact]

If an ongoing SAE changes in its intensity or relationship to study drug or if new information becomes available, a follow-up SAE report should be sent within 24 hours to the BMS using the same procedure used for transmitting the initial SAE report. All SAEs should be followed to resolution or stabilization.

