3.2 SAFETY ENDPOINTS

Safety assessment will include adverse events, vital signs, physical examination findings, laboratory parameters and NCI common terminology safety assessment, including focus on serious adverse events and the infection module. This will be collected in person during study visits, but in between study visits, a phone call will be made at weeks 2, 4,8,10,14,16, 20 and 22 to review adverse events.

Patient evaluations include:

1. Vital sign measurement, physical examination

2. Laboratory parameters for hematology, routine chemistry, muscle enzymes and urinalysis
3. NCI Common Toxicity assessment (version 4.0 June 2010) including focus on serious adverse events and the infection module.
4. Adverse event monitoring
5. Assessment of primary and secondary efficacy endpoints

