- Collect blood samples prior to the injection at Week 24 for PK and immunogenicity assessment
- Prednisone taper may commence using a predetermined schedule (section 5) if the patient has achieved the Definition of Improvement (DOI) and is rated by the study physician as at least minimally improved.
- Administer dose of study medication (abatacept) and observe after the injection for at least 15 minutes
- Patient terminates study enrollment and all study supplies are returned, or patient will continue on open-label extension: schedule and instruct the subject to return for the next visit

- An open label extension phase will be offered for up to 6 months for patients meeting the definition of improvement and who are rated by their study physician as at least minimally improved.
- If the subject chooses not to continue to be in the open label extension phase of the trial, the subject will be referred back to his/her local rheumatologist for further care. Subject terminates study enrollment and all study supplies are returned
- Subjects will receive their last injection of abatacept at week 24 even if they do not want to continue in the open label extension phase of the trial

Open label extension Visit (will occur within 6 months of visit 5)

An open label extension phase of up to 6 months duration will be offered to all patients meeting the definition of improvement and who are also rated as at least minimally improved from the baseline visit (visit 1). Patients must commit to at least one follow-up visit within 6 months of visit 5, which will be at their own expense for travel and testing costs. At each follow-up visit, the following will be performed:

- Review concomitant medication and query for adverse events and document in CRF.
- NCI Common Toxicity Assessment
- Obtain vital signs (HR,BP,RR, oral temperature and weight) and if indicated , by history of shortness of breath or lung disease, pulse oximetry)
- Medical history and perform a full physical examination
- Collect urine sample for pregnancy test for females of child bearing potential prior to administration of study medication (where applicable)
- Core set activity measures: physician global activity, patient/parent global activity, manual muscle testing (MMT-8), CMAS, HAQ/CHAQ,MDAAT, muscle enzymes, CHQ PF-50/SF- 36, and Disease activity score (DAS), physician global damage (VAS)
- Physician and patient/parent assessment of study outcome

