APPENDIX E TABLE 1 AND TABLE 2 /2a: STUDY SCHEDULE OF EVENTS

Table 1.

Study Events	Treatment Week														
	Screening	W0	W2	W4	W6	W8	W10	W12	W14	W16	W18	W20	W22	W24	W25-W48
Visit	V1				V2			V3			V4			V5	V6 (extension)
Phone f/up*			X	X		X	X		X	X		X	X		
Informed Consent/Assent	X														
Inclusion/Exclusion Criteria	X														
Vital signs, Weight, (pulse oximetry) is changed to screening evaluation	X	X			X			X			X			X	X
Brief physical evaluation		X			X			X			X			X	X
CMAS	X	X			X			X			X			X	X
MMT8	X	X			X			X			X			X	X
MDAAT (EM Global only at Screening)	X	X			X			X			X			X	X
Disease Activity Score		X			X			X			X			X	X
MD Global Activity (VAS)	X	X			X			X			X			X	X
Patient/Parent Global Activity (VAS)	X	X			X			X			X			X	X
CHAQ/HAQ	X	X			X			X			X			X	X
CHQ-PF50/SF36		X			X			X			X			X	
Myositis Damage Index		X												X	
Urine Pregnancy , UA,	X	X			X			X			X			X	X
Screening Blood Tests	X														
Research Blood Tests form is changed to blood sample tracking form (regular and research blood test)		X						X						X	
Chest X-ray	X														
Plain radiograph for calcinosis (calcinosis pts only)		X												X	
Muscle MRI (bilateral, Axial and T1)		X												X	
MD Global Disease Damage (VAS)		X			X			X			X			X	X
Physician Assessment of Study Outcome					X			X			X			X	X

Dermatology assessment ([name] Global Skin Activity/Damage performed by Dermatologist) Optional		X						X						X	
CDASI (performed by Rheumatologist)		X			X			X			X			X	X
DLQI, skin itch, Patient and MD skin global activity/damage (performed by Rheumatologist)		X			X			X			X			X	X
Photograph Documentation (if applicable)		X			X			X			X			X	X
Nailfold capillaries photograph (Optional)		X						X						X	X
PROMIS and PedsQL fatigue		X			X			X			X			X	X
Review medication log and self-administration log		X			X			X			X			X	X
NCI CTC Assessment		X			X			X			X			X	X
Adverse Events assessments		X	X	X	X	X	X	X	X	X	X	X	X	X	X
Prednisone taper if meet DOI and rated at least minimally improved					X			X			X			X	X
Increase Abatacept dose if ≤ 5% improved by DOI and rated as unchanged or worsened								X							
Administer Abatacept medication		X			X			X			X			X	X
Visit		V1			V2			V3			V4			V5	V6
Week	Screening	W0	W2	W4	W6	W8	W10	W12	W14	W16	W18	W20	W22	W24	W25-W48

*Phone f/up at W2, 4, 8, 10, 14, 16, 20, and 22 will consist of evaluation of Adverse Events.

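### SAEs must be collected for 30 days after dosing stops, but no contact is scheduled after the final dose at week 24 or at the end of the extension

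*Combined protocol and SAP*

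**What the plan says.** **The requirement.** The SAE text under Section 12.3 states: "All SAEs must be collected that occur within 30 days of discontinuation of dosing". It covers related and unrelated events. It does not say how events after the last dose are to be found.

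**The last dose.** Section 7.1, Visit 5, says: "Subjects will receive their last injection of abatacept at week 24 even if they do not want to continue". The same visit lists: "Administer dose of study medication (abatacept) and observe after the injection for at least 15 minutes". For a patient who declines the extension, the text then says that "the subject will be referred back to his/her local rheumatologist for further care", and: "Subject terminates study enrollment and all study supplies are returned".

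**The scheduled contacts.** Section 3.2 describes safety data as collected in person at visits, and between visits "a phone call will be made at weeks 2, 4,8,10,14,16, 20 and 22 to review adverse events". The footnote to Appendix E, Table 1 gives the same list: "Phone f/up at W2, 4, 8, 10, 14, 16, 20, and 22 will consist of evaluation of Adverse Events". Adverse events are also queried at each visit, including Visit 5. The only later column in the table is the extension visit, for weeks 25 to 48.

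**The extension.** Section 7.1 requires at least one visit within 6 months of Visit 5. That visit includes a dose, after which the extension ends and the patient returns to the referring rheumatologist.

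**Early stoppers.** Section 9.0 encourages anyone who has had at least one dose to go on attending visits and calls so that safety can be followed.

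**The concern.** A mandatory collection window needs some means of finding the events in it. During treatment this protocol has a good one: a visit or call every two weeks. The window after treatment has none, because for patients who leave at week 24 the final dose and the final contact are the same appointment.

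Safety is half of the primary objective (Synopsis, Sections 2.1 and 3.1), and Section 2.1 gives particular attention to serious adverse events and infections. With 10 patients, each patient with an SAE is 1/10, or 10 percentage points, of the patient-level SAE proportion. The rule that pauses enrolment when 3 or more patients have a related SAE (Sections 9.0 and 13.0) also works only on events that reach the investigator. If follow-up SAEs are not sought, the report cannot separate a patient who had no event from one who was not asked.

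**Working it through.** The check is schedule arithmetic. No power or error-rate figure is involved.

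**Inputs**
- Visits at weeks 0, 6, 12, 18 and 24 (Sections 3.0 and 7.1; Appendix E).
- Calls at weeks 2, 4, 8, 10, 14, 16, 20 and 22 (Section 3.2; Appendix E).
- Last dose at Visit 5, week 24 (Section 7.1).
- SAE window of 30 days after dosing stops (Section 12.3).

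**1. Contacts on treatment.** 5 visits + 8 calls = 13 contacts, at weeks 0, 2, 4, …, 24. Each gap is 2 × 7 = 14 days. The last contact is on day 24 × 7 = 168.

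**2. The window for a patient stopping at week 24.** It runs from day 168 to day 168 + 30 = 198. Scheduled contacts after day 168: none. Days covered by a scheduled contact: 0 of 30. The only observation after the dose is the 15 minutes in clinic.

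**3. Share of the at-risk period.** 30 / (168 + 30) = 30/198 = 0.152, or 15%.

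**4. Visit windows.** Each interval may vary by 10 days, so Visit 5 can fall up to 4 × 10 = 40 days either side of day 168 (day 128 to day 208). This moves the start of the window but not the result, because the dose is given at the visit.

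**5. Number of patients.** The documents do not give it. The hypothesis is that at least 6 of 10 meet the improvement definition, so non-responders on that definition would be at most 10 − 6 = 4. Extension entry also needs a physician rating of at least minimal improvement, and eligible patients may decline, so the number stopping could be higher. Over an assumed range:

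| Patients stopping at week 24 | Mandatory patient-days with no scheduled contact |
|---|---|
| 1 | 30 |
| 4 | 120 |
| 10 | 300 |

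**6. End of the extension.** If the dose listed at the extension visit is the patient's last, the count is again 0 of 30, since nothing is scheduled afterwards.

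**7. Early stoppers.** Suppose the last dose is on day d and the patient keeps attending to day 168. A contact at or after day 30 exists if d + 30 ≤ 168, that is, d ≤ 138. On nominal weekly dosing, a last dose at week 19 (day 133) is covered. A last dose at week 20 (day 140) or later is covered only in part.

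**8. With one added call.** A call on day 198 to day 205 (168 + 30 to 168 + 37) that asks about the time since Visit 5 raises coverage from 0 of 30 to 30 of 30 days.

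**The case against.** The best defence is that a rule to collect events need not be carried out by a scheduled contact. Section 12.1 says: "Adverse events will be tracked through routine communication with the subjects and the family". Section 12.2 refers to a Manual of Operations for reporting procedures. Inclusion criterion 15 requires a letter from the supervising specialist agreeing to continue care, and screening records the referring physician's details and a release to share information. Many SAEs involve hospital admission, which that physician may well learn of.

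This stands as a reason for caution about consequences. It does not fill the gap. The communication statement names no time point. The Manual was not available for this review, and the protocol cites it for reporting, not for added contacts. The letter covers participation and care, and states no duty to report SAEs to the study.

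A reader might infer several stronger things that the documents do not support:
- **Late SAEs will be missed, or the window rests wholly on unsolicited reports.** Informal channels may bring events in. The supportable statement is that no contact is scheduled, so events can be missed.
- **The safety result is biased downward.** Section 2.1 compares adverse events in the 6 months before enrolment with those after abatacept starts. It defines no post-treatment analysis period, and the plan gives no event rate for that window. Neither the direction nor the size of any effect on the reported result is shown.
- **Only non-responders and decliners are affected.** Responders who finish the extension also have no contact after their last listed dose.
- **The gap opens at week 22, after the last call.** Adverse events are queried again at Visit 5, so it opens at week 24.
- **All early stoppers are unfollowed.** Section 9.0 encourages them to stay in contact, and those who do so may already be covered.

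**Conclusion.** The point holds as a mismatch between a mandatory 30-day SAE window and a contact schedule that ends with the final dose, both at week 24 and at the end of the extension. For a patient stopping at week 24 it affects 30 of 198 nominal days (15%), none with a scheduled contact. On the improvement definition alone this would be up to 4 of 10 patients under the protocol's hypothesis. The true number is not stated and could be larger.

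This rests on two assumptions: that the protocol and Appendix E contain the full contact schedule, and that the dose at the extension visit is the patient's last. If the Manual of Operations already sets a 30-day contact, the gap is one of protocol wording only. The consequence is possible under-ascertainment for a primary safety objective, not a demonstrated bias. The change is worth making because it is specific and costs little.

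**What to change.** In Section 7.1 and Appendix E, Table 1, add one adverse-event phone call 30 days (+7) after the last dose for every patient who has no other scheduled contact at or after day 30. This covers patients who stop at week 24, patients who end the extension, and early stoppers whose remaining visits and calls do not reach day 30. The existing call format can be used, asking about the whole period since the last contact. The statements in Section 7.1 that participation ends at Visit 5 or at the extension visit should be aligned, so that SAE collection clearly runs until this call.

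The cost is about one extra call per patient, by staff who already plan eight for each, and a last contact date 30 to 37 days after the final dose. No dose, treatment rule or efficacy assessment changes.

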13.0 DATA SAFETY MONITORING PLAN

The Data Safety and Monitoring Board (DSMB) will be appointed under the direction of (to be named). DSMB members have no potential financial conflicts of interest. Written documentation attesting to the absence of conflict of interest will be required of all DSMB members on an annual basis. The ongoing review of data by this independent committee assures the investigators that the trial can continue without jeopardizing patient safety.

The DSMB will review the study protocol, recommend recruitment initiation, monitor all aspects of study (e.g., recruitment, protocol deviations, adverse events, data quality, descriptive characteristics, efficacy) and recommend protocol modifications, including early study termination.

Meetings of the DSMB will occur on an annual basis to review all aspects of the study (e.g., recruitment, adverse events, and efficacy). In addition, reports will be produced to show study progress according to a set schedule dictated by the DSMB. The DSMB will also receive reports of any serious adverse events within 24 hours and review together if 3 or more patients develop SAEs thought likely to be related to study drug.

14.0 ASSESSMENT TOOLS: description

The core assessment tools are available on the International Myositis Assessment and Clinical Studies (IMACS) Group website at:

1. IMACS website:
<http://www.niehs.nih.gov/research/resources/imacs/imacsforms/>
2. Disease activity core set measures:
<http://www.niehs.nih.gov/research/resources/imacs/diseaseactivity/index.cfm>
3. Disease damage core set measures:
<http://www.niehs.nih.gov/research/resources/imacs/diseasedamage/index.cfm>

Manual Muscle Testing. (MMT): MMT has been widely used in myositis therapeutic trials and clinical studies, previously as a primary end point (17) and more recently as part of a composite end point of core set measures (38). MMT has been modified to a shorter version called MMT-8, in which quantitative testing of eight proximal, distal and axial muscle groups tested unilaterally (using a 0-10 point scale) closely approximate a total MMT score of 26 groups tested bilaterally(42).

MMT- 8 is a set of 8 designated muscles tested unilaterally (potential score 0-80) or bilaterally (potential score 0-150)

Muscle Groups	Right (0 – 10)	Left (0 – 10)	Axial (0 – 10)
Axial Muscles (0 – 10)			
Neck Flexors	X	X	0-10
Proximal Muscles (0 – 100)			
Deltoid	0-10	0-10	X
Biceps brachii	0-10	0-10	X
Gluteus maximus	0-10	0-10	X
Gluteus medius	0-10	0-10	X
Quadriceps	0-10	0-10	X
Distal Muscles (0 – 40)			
Wrist Extensors	0-10	0-10	X
Ankle dorsiflexors	0-10	0-10	X
MMT-8 score (0 – 150)	0-70	0-70	0-10

Myositis Disease Activity Assessment Tool (MDAAT). This tool has been developed by IMACS. This is a comprehensive tool that captures the physician’s assessment of disease activity of muscle, skin, joints, gastrointestinal tract, lung, and other organ systems. The MDAAT is a combined tool that includes the Myositis Disease Activity Assessment Visual Analog Scale (MYOTAC) and the Myositis Intention to Treat activities Index (MITAX).

The MYOACT is a series of physician’s assessments of disease activity in various organ systems using a VAS to assess severity of activity that has been modified from the Vasculitis Activity Index (42) The MYOACT consists of a 10-cm VAS for each organ system to score the overall severity of activity in each and a global extra-muscular VAS. For the MYOTAC, each organ system has a single VAS; a global extra-muscular activity VAS is also scored.

The MITAX assesses specific manifestations in 7 organs/systems, including constitutional, cutaneous, skeletal, gastrointestinal, pulmonary, cardiac, and muscle. For the MITAX each question is answered as 0= not present; 1= improving, 2= the same, 3= worse, 4=new.

The key issue in relation to the MDAAT is to ensure that the items recorded are, in view of the physician, actually due to the active myositis and not due to disease damage, another unrelated process, or a side effect of medication.

Disease Activity Score (DAS): this tool assesses muscle and cutaneous manifestations, including vasculopathic features, based on bedside clinical assessment. The DAS consists of 19 items, resulting in a score of 0-20: 1) the presence or absence of weakness is assessed via 8 variables: neck flexors muscles, abdominal muscles, upper extremity proximal muscles, lower extremity proximal muscles, Gower's sign, abdominal gait, difficulty swallowing, and nasal speech. 2) Functional status consists of a 4-point scale, ranging from normal function to severe limitations in daily life functions. 3) The presence or absence of vasculitis is assessed by determining the presence of any one of the following: eyelid erythema, eyelid vessel dilatation, eyelid thrombosis, nailfold erythema, nailbed telangiectasia, dilatation of blood vessels on the palate, and "other vasculitis". 3) The presence of rashes is rated using polychotomous scales: the distribution of the involved skin is rated on a 4-point scale ranging from none to generalized, while the severity of skin involvement is rated on a 5-point scale, ranging from absent to severe. Gottron's papules are rated on a 4-point scale,(42)

Muscle Enzymes: Activity of at least one serum muscle enzyme from the following: creatine kinase (CK), aldolase, lactate dehydrogenase (LDH), alanine aminotransferase (ALT) and aspartate aminotransferase (AST). The most abnormal muscle enzyme will be chosen as the core measure to be followed.

MDI: Myositis Damage Index: The MDI scores damage, which is defined as persistent or permanent change in anatomy, physiology, and function that develops from previously active disease, complications of therapy, or older events.(42). The MDI measures specific manifestations in 11 organ systems. The MDI also includes a series of visual analog scales (VAS) to quantify damage severity in a given organ system.

Stanford HAQ/CHAQ: Health Assessment Questionnaire: The Stanford HAQ is a brief self-report questionnaire assessing physical function pertaining to activities of daily living in a variety of domains (42). Originally developed for use in rheumatoid arthritis, it has been successfully applied inflammatory myopathies. The C-HAQ was adapted directly from the HAQ and it has also been successfully applied to patient with juvenile myositis. (42).

Physician Global Assessment (MD Global Activity): It is a tool that measures the global evaluation by the treating physician of the overall disease activity of the patient at the time of assessment using a 10 cm. visual analogue scale and a 5 point Likert scale, validated by JDM study group.(43)

Patient/Parent Global Assessment Patient/Parent Global Activity, 0- 10 cm VAS.

It is a tool that measures the global evaluation by the patient, or by the parent if the patient is a minor, of the patient's overall disease activity at the time of assessment using a 10 cm. visual analogue scale. (Validated by JDM study group (43)

Childhood Myositis Assessment Score (CMAS) is validated tool to assess muscle strength, physical function, and endurance. Items of the CMAS include upper and

lower extremity muscle groups, simple and compound movements, and timed items to evaluate endurance. The tool is weighted toward lower extremity proximal and axial muscle groups more than upper extremity and distal muscle groups. The CMAS consists of 14 items. The CMAS has been included as a core set activity measure by both the IMACS and PRINTO (42)

Assessment to be performed by the Dermatologist is Optional: Cutaneous Dermatomyositis Disease Area and Severity Index (CDASI) It measures activity and damage in the skin. The modified CDASI (version 2) is the one in current use. It has 3 activity scales (erythema, scale, erosion/ulceration) and 2 damage measures (poikiloderma and calcinosis). In addition, Gottron's papules on the hands are evaluated in terms of activity (erythema/ulceration) and damage (dyspigmentation or scarring). Activity in terms of periungual changes and alopecia is also measured. Each of the 3 activity scales and 2 damage measures is assessed over 15 body areas; the worst level of activity is scored, whereas the damage measures is scored for their presence or absence. It will be performed by both Rheumatology and Dermatology. (42)

Childhood Health Questionnaire (CHQ) is validated tool to assess health related quality of life, physical and psychosocial well-being of children at least 5 years of age. The CHQ consists of 14 health concepts: global health, physical functioning, role/social limitations-emotional/behavioral, role/social limitations-physical, bodily pain/discomfort, behavior, general behavior, mental health, self-esteem, general health perception, parent impact-emotional. Parent impact-time, family activities, and family cohesion. In addition, there are 2 summary measures, the Physical summary score (PhS) and the Psychosocial summary score (PsS). The CHQ- PhS has been selected by PRINTO as a core set of measures to be used to evaluate response to therapy in JDM. (42)

SF-36 is a widely used tool that assesses the global medical quality of life, functional health and well-being. It has been used in several small natural history studies of PM and DM (44)

Dermatology Life Quality Index (DLQI). It is a simple questionnaire to assess quality of life in skin disease. The measure consists of 10 questions related to skin symptoms and feelings, daily activities, leisure, work or school, personal relationships, and the side effects of treatment. Each item is scored on a Likert scale, where 0= not at all/not relevant, 1= a little, 2= a lot, 3=very much. (42)

PROMIS and Peds QL Fatigue Questionnaires: The PROMIS Fatigue instruments evaluate a range of self-reported symptoms, from mild subjective feelings of tiredness to an overwhelming, debilitating, and sustained sense of exhaustion that likely decreases one's ability to execute daily activities and function normally in family or social roles. Fatigue is divided into the experience of fatigue (frequency, duration, and intensity) and the impact of fatigue on physical, mental, and social activities. The fatigue short form is generic rather than disease-specific. It assesses fatigue over the past seven days.

The PedsQL Multidimensional Fatigue Scale was designed to measure fatigue in pediatric patients, but can also be used in adults. It is comprised of the General Fatigue Scale (6 items), Sleep/Rest Fatigue Scale (6 items), and Cognitive Fatigue Scale (6 items).

Fatigue instruments are available for adults (ages 18+), pediatric self-report (ages 8-17) and for parents serving as proxy reporters for their child (youth ages 5-17).

Assessment of Study Outcomes: A physician assessment of whether the patient has improved or worsened from baseline, and by how much (mild, moderate, great degree of change) will be made at each follow-up visit, using the IMACS assessment tool available for this outcome.

